a. Substrate kinetics and insulin sensitivity. Glucose and palmitate kinetics during the clamp procedure will be used to provide an index of hepatic, skeletal muscle and adipose tissue insulin sensitivity, as we previously described [31, 38, 39]. Glucose Ra in plasma during basal conditions and the clamp procedure will be calculated by dividing the glucose tracer infusion rate by the average plasma glucose TTR during the last 30 min of the basal and clamp periods, respectively. Glucose Ra during basal conditions represents endogenous glucose Ra, an index of hepatic glucose production rate, which equals basal glucose rate of disappearance (Rd). During the clamp procedure, hepatic glucose production rate will be calculated by subtracting the glucose infusion rate (i.e., dextrose solution plus tracer added to it) from total glucose Ra (endogenous plus exogenous); glucose Rd is equal to total glucose Ra (i.e., the sum of endogenous glucose Ra and the rate of infused glucose). Palmitate Ra, an index of adipose tissue lipolysis will be calculated by dividing the palmitate tracer infusion rate by the average plasma palmitate TTR obtained during the final 30 min of the basal period and insulin infusion.

b. β -cell function. Insulin secretion rate (ISR) during the modified 3-h oral glucose tolerance test (MOGTT) will be calculated by stochastic deconvolution analysis of the plasma C-peptide concentration time-course [40]. β -cell response sensitivity to glucose will be assessed as the ratio of the area under the curve (AUC) of ISR (pmol/L) to the AUC of glucose [41-43]. β -cell function in relation to insulin sensitivity will be assessed based on the principle of the disposition index, calculated as the product of the area under the curve (AUC) of ISR (pmol/L) assessed during the MOGTT and the rate of insulin-stimulated glucose disposal normalized for plasma insulin concentration ($\mu\text{mol/kg FFM/min per } \mu\text{IU/mL}$) assessed during the hyperinsulinemic euglycemic clamp procedure, as we have previously reported [20]. Insulin secretory reserve will be assessed by measuring the AUC of insulin and ISR over 10 min after the intravenous administration of 5 g of arginine [44, 45].

C.3.9. Sample analyses.

All sample analyses are routinely performed by our research group or in our Core laboratories at Washington University School of Medicine.

a. Plasma concentrations of substrates and hormones and markers of inflammation will be measured by our Core Laboratory for Clinical Sciences, as we have previously described [30, 32].

b. Plasma glucose and palmitate tracer-to-tracee ratios will be determined by using gas chromatography-mass spectroscopy, as we have previously described [46].

c. Plasma NMN and nicotinamide, PBMC NAD^+ and tissue NAD^+ , nicotinamide and ATP. Plasma NMN and nicotinamide and tissue NAD^+ , nicotinamide, and ATP concentrations will be determined by using an HPLC system (Prominence; Shimadzu) with a Supelco LC-18-T column (Sigma) and a Hypercarb column (Thermo Scientific), as we have previously described [2, 5, 7, 14, 47-51].

d. Adipose tissue gene expression of inflammatory markers (*IL6*, *TNF*, *MCP-1*, *IL1 β* , *EMR1*, *CD68*) and adiponectin (a key downstream target of adipose tissue NAD^+ [7]) will be determined by using Real time-PCR. Total RNA will be isolated from frozen adipose tissue biopsy samples in RNeasy kit (Qiagen, Valencia, CA) and reverse transcribed (High-Capacity cDNA Reverse Transcription Kit; Invitrogen, Carlsbad, CA) [30, 32,

52-56]. Tissue gene expression was determined using an ABI 7500 real-time PCR system (Invitrogen) and SYBR Green Master Mix (Invitrogen), as we have previously described [30, 32, 53]. The expression of each gene will be normalized to the housekeeping control gene, ribosomal protein (*RPLP0*).

e. Skeletal muscle transcriptome analysis by using RNA-seq. Total RNA will be isolated from frozen skeletal muscle biopsy samples in Trizol reagent (Invitrogen), as we have previously described [53-55, 57]. We will first evaluate the effects of NMN supplementation on muscle gene expression of specific NAD⁺ downstream targets (mitochondrially encoded genes, *ND1-ND6*, *Cytb*, *COX1*, *COX2*, *COX3*, *ATP6*, *ATP8*) [16] and inflammatory markers (*IL6*, *TNF*, *MCP-1*, *IL1 β* , *EMR1*, *CD68*) by using Real time-PCR as described above.

f. Assessment of insulin signaling and NAD⁺ downstream targets. Western blot analysis will be performed to evaluate the muscle content and phosphorylation of intracellular proteins involved in the insulin signaling cascade (AKT and AMPK) as we previously described [52, 54, 58]. We will also evaluate muscle content of proteins involved in the electron transport complex [14, 59] and global protein acetylation status, and a key NAD⁺-SIRT1 downstream target, acetyl-NF- κ B p65 [5, 7, 48]. Blots will be probed with polyclonal and monoclonal antibodies including anti-phospho-AKT (Ser473) (#4060; Cell Signaling Technology), anti-total-AKT (#4691; Cell Signaling Technology), anti-phospho-AMPK α (Thr172) (#2535; Cell Signaling Technology), anti-total-AMPK α (#2532; Cell Signaling Technology), anti-acetylated lysine (#9441; Cell Signaling Technology), anti-acetyl-NF- κ B p65 (Lys310) (#3045; Cell Signaling Technology), and anti-total OXPHOS cocktail (#ab110413; Abcam).

D. Statistical plan and Data analysis

Statistical evaluation of the study data will be carried out in collaboration with [name], who is an applied biostatistician with expertise in the design and analysis of clinical trials. Our primary analysis will be intention-to-treat in people with prediabetes. Preliminary analyses involving t-tests or Wilcoxon's test for continuous variables and chi square tests for dichotomous variables will be performed to confirm that baseline characteristics of subjects are similar in the placebo and NMN treatment groups. ANCOVA with the post-treatment value of the metabolic outcome measure (e.g., our primary outcome variable is insulin-mediated glucose uptake) as the dependent variable will be used to determine whether there are between group differences in the outcome measure after adjusting for the pre-intervention value and any measures that were significantly different before or during the intervention. We will explore the distributional properties of the metabolites; if the variables are skewed, we will analyze the data following a data transformation (e.g., a log transformation). If an appropriate transformation cannot be found, we will analyze the data semi-parametrically by using the ranks of the data. An exploratory goal of this study is motivated by preliminary data from rodents suggesting that the efficacy of NMN on the primary outcome may be greater in female than male animals. Therefore, we will evaluate the interaction between sex and treatment group by using analyses of covariance. These analyses should provide evidence regarding the possibility that efficacy differs according to the sex of the individual. We emphasize the exploratory nature of these analyses. This study is not powered to evaluate the relevant interaction term, and our purpose is to generate preliminary data to determine whether a subsequent larger study to assess the response to NMN based on sex is worthwhile.

Sample size considerations. The single primary endpoint in this study is insulin-mediated glucose Rd. All other endpoints are secondary. Because there is only one primary endpoint, the power computations for that endpoint are not adjusted for multiple testing. We also present power computations for important secondary endpoints below, but emphasize that the target sample size is based on considerations related to the primary outcome only.

Using G*Power 3.1.9.2 and day-to-day variance we have previously reported in similar intervention studies [38, 60], we estimated that 22 participants/group will be needed to detect *realistic and physiologically and clinically meaningful* between-group differences in insulin-mediated glucose Rd [61, 62] with >90% power using a two-sided test and an α value of 0.05 in all primary outcomes listed below. Therefore, we will enroll 28 participants

in each group to ensure that an adequate number of participants complete the study (allowing for an estimated 6 drop-outs/group). All of the power computations below are based on a power of 0.9.

Insulin-mediated glucose Rd. We have reported day-to-day variability in insulin-mediated glucose Rd during high-dose insulin infusion (means \pm SD) to be 3.4 ± 6.1 $\mu\text{mol/kg FFM/min}$ in people with prediabetes. Using these SDs and assuming similar variance in the placebo and NMN groups, we estimate we will be able to detect a ~ 6.2 $\mu\text{mol/kg FFM/min}$ difference between groups in subjects with prediabetes ($\sim 14\%$ difference based on an expected mean glucose Rd at baseline of 44.5 $\mu\text{mol/kg FFM/min}$) [61].

Tissue gene expression. It is difficult to make robust estimates of our study power to detect changes in the molecular outcomes in adipose tissue and muscle, because of limited data evaluating these variables and the unknown effects of altering sleep. However, in our own experience, the day-to-day variance in muscle and adipose tissue gene expression is $\sim 30\%$ [52]. Accordingly, we estimate that we have $\geq 90\%$ power to detect statistically significant effect of NMN therapy in both people with prediabetes, if the differences from placebo are $>30.5\%$. Our previously published data [61] indicate that differences in adipose tissue gene expression of this magnitude are *realistic* in response to dietary and pharmacological intervention. Our study also has other (secondary) outcomes listed in Section C.3.1.b. These outcomes are important and we believe they will generate important information. However, it is difficult to estimate statistical power for these outcomes because of inadequate available information.

E. Retention and Recidivism plan.

Participants will be provided with a monthly pill organizer coded by days of the week after completing baseline testing, to help improve adherence to take individual doses of dietary supplementation each day. In addition, participants will be provided with a dietary supplementation diary with dates between study visits to keep track of the daily dietary supplementation record. Participants will be asked to bring this handout to each intervention visit. Several strategies will be used to enhance adherence with the study protocols and reduce drop-outs: i) a philosophy of partnership and collaboration will be encouraged between research site personnel and study participants; ii) reimbursement for time required for study visits will be provided; iii) participants will be contacted weekly by the research coordinator and/or research nurse; and iv) participants who are not adhering to the study protocol will receive additional support by the study team with an intervention plan established after reviewing the participant's specific barriers for compliance.

H. Protection Against Risk

Medical screening will include laboratory safety evaluation, including Complete Blood Cell count [CBC] (which include red blood cell count), Complete Metabolic Panel [CMP] (which include electrolytes, renal function tests and liver biochemistries), HbA1c (which indicates plasma glucose control), and PT-INR (which indicates coagulation disorders), and history and physical examination to screen out those who have increased potential risks. Participants will be questioned in detail about medical history including metal placement in the body and claustrophobia.

Only skilled nursing staff (Nurse practitioners and RNs) will be used to placement of intravenous and arterial catheters. Only skilled nurse practitioners and physicians will perform abdominal fat and thigh muscle biopsy.

Safety monitoring during intervention period will include measurement of blood pressure and evaluation for any adverse effects with a study team member. Intravenous tracer solutions will be prepared in a designated, sterile

mixing room, by a certified pharmacy technician who completes annual recertification through BJH Pharmacy and is also GMP certified. Careful aseptic techniques will be used when inserting the catheters and when obtaining blood samples to decrease the risk of infection. In addition, continuous safety monitoring will be completed by [name] (PI) on a bi-monthly basis in person or remotely. All laboratory data and adverse events will be collected by the research nurse practitioner and the research investigator and will be reviewed and discussed by [name] (PI).

At time of informed consent each participant will be assigned a unique participant identifying number (study ID) and the link between ID and PHI will be kept in the REDCap. Consent forms and any other paper forms for the study will be stored in a locked filing cabinet in the office

The study ID is not related information about the individual and is not capable of being translated so as to identify the individual. Data and biological samples collected from study participants during the study participation will be labeled with the study ID and will *not* be used in combination with any personal identifiable information (PII).

All of the requested information as part of this study including PHI will be treated confidentially, protected from improper use and disclosure and will not be reused or disclosed to any other person or entity, except as required by law, for which the use or disclosure of the requested information would be permitted by the HIPAA Privacy Rule.

The use of 38 U.S.C. 7332 Information is to conduct scientific research and that no personnel involved may identify, directly or indirectly, any individual patient or subject in any report of such research or otherwise disclose patient or subjects in any manner.

The PII obtained from human subjects will only be available to individuals approved by WUSM IRB (only after participant signed WU informed consent form). Subject research records will be secured in areas under the 2-key lock concept (e.g., in a locked cabinet with access limited to the study team members in a locked room) at WUSM (Suite 301 at IWJ building). Electronic records (e.g., computer files and database) that contain PHI will be stored on firewall-protected secured servers at WUSM facilities that require approved access authorization.

Data Transfer/Sharing Plan

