- 2. Baseline Testing.** There are three test visits. Visit 1 is an inpatient visit that includes a hyperinsulinemic-euglycemic clamp procedure, adipose tissue and muscle biopsies, Arginine stimulation test, and a 12-h urine collection. An activity monitor will be provided to the participant that will be worn for the proceeding 7 to 10 days. Visit 2 is an outpatient visit where dual-energy X-ray absorptiometry and magnetic resonance imaging/elastography scans will be performed and muscle strength will be assessed. Visit 3 is another inpatient visit that involves a modified 3-h oral glucose tolerance test and the first dose of study pill ingestion. A stool sample will also be returned to the study team at Visit 3. The scans performed during visit 2 may be performed at a different or separate visit, depending on scheduling availability and participant preference.
- 3. Randomization.** Randomization will be conducted in a double-blind fashion with both the participants and members of the research team blinded to group assignment.

4. **Intervention period.** During the 16 weeks of the treatment period, participants will be seen by the research coordinator and/or one of the study investigators each week. At each visit at WU, compliance will be recorded based on an unused pill count.
5. **Repeat testing.** All baseline testing will be repeated after participants complete 16 weeks of treatment.

A. Background and Significance

Nicotinamide mononucleotide is a key intermediate for nicotinamide adenine dinucleotide (NAD⁺) biosynthesis

Nicotinamide adenine dinucleotide (NAD⁺) is a co-substrate for NAD⁺-consuming enzymes that are essential in the regulation of diverse biological processes, including metabolic function, inflammation and aging [1-4]. In mammals, NAD⁺ is synthesized from nicotinamide (NIC) and nicotinic acid (two different forms of vitamin B₃) and tryptophan (Figure 1). Nicotinamide is considered the major precursor of NAD⁺. Nicotinamide mononucleotide (NMN) is a key NAD⁺ intermediate which is synthesized from NIC by nicotinamide phosphoribosyltransferase (NAMPT), a rate-limiting NAD⁺ biosynthetic enzyme. Nicotinamide riboside (NR) is also converted to NMN by nicotinamide riboside kinases (NRKs). NMN is converted to NAD⁺ by three NMN adenylyltransferases (NMNATs). Synthesized NAD⁺ is used by NAD⁺-consuming enzymes, such as sirtuins (SIRT1-7), poly (ADP-ribose) polymerases (PARPs), and cyclic ADP ribose hydrolase (CD38), and redox reactions.

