Little is known about NAD⁺ biology and NMN therapy in people. Data from preliminary studies we recently conducted in human subjects show that enhanced NAD⁺ biosynthesis is associated with metabolic health in people: i) adipose tissue NAD⁺ content is lower in people with obesity than people who are not obese (Figure 3A); ii) 16% weight loss induced by lifestyle (diet and exercise) therapy improved insulin sensitivity and β -cell function and decreased intrahepatic triglyceride (IHTG) content and caused a concomitant increase in skeletal muscle gene expression of a key NAD⁺ biosynthetic enzyme, NAMPT, in people with obesity and T2D (Figure 3B); and iii) 20% bariatric surgery-induced weight loss, which improved insulin sensitivity, β -cell function, and adipose tissue inflammation and decreased IHTG content in people with extreme obesity [20], also increased NAD⁺ concentrations in adipose tissue (Figure 3C). Although NMN is present in a variety of natural foods, including broccoli, tomatoes, avocado, and beef [14], the daily amount of NMN that is normally consumed as part of a healthy diet is very small. We found that ingestion of a single 250 mg dose of NMN, which is at the upper end of the dose typically taken by consumers, caused a rapid but transient increase in plasma NMN concentrations (Figure 4A) but caused more than a 3-fold increase in peripheral blood mononuclear cell (PBMC) NAD⁺ content within 60 minutes (Figure 4B). The dose of NMN used in the proposed study is 300 or 450 mg/day.

Summary. Data obtained from preclinical studies we conducted in rodent models and our preliminary studies conducted in people support the therapeutic potential of enhancing NAD⁺ biosynthesis to ameliorate metabolic dysfunction in people. In fact, NMN supplementation is commercially available, and is advertised to improve health and reverse aging, without evidence of these effects in people. The goal of this proposal is to fill this important gap in our knowledge by using a systems biology research approach, within the context of a randomized, placebo-controlled trial, to determine whether the beneficial effects of NMN on metabolic function, mitochondrial function and inflammation observed in rodents applies to people. In addition, we will evaluate for potential sex differences in the efficacy of NMN supplementation (observed in studies conducted in rodents) by studying a balanced number of men and women in each group.

B. Objectives/Specific Aims/Hypotheses

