This study will be conducted as a randomized, placebo-controlled, double-blind trial, and both the participants and members of the research team directly involved with study participants and data analysis will be blinded to group assignment. Participants will be admitted to the inpatient CTRU on two occasions to complete baseline testing. Each of these visits will be scheduled ~5-10 days apart. Subjects will be asked to avoid caffeine and alcohol for at least 24 h, and to abstain from any structured intense exercise for 3 days before each admission. After participants complete baseline testing, they will be randomly assigned to treatment with either placebo or NMN, taken daily after breakfast for 16 weeks. *Placebo and NMN capsules will be provided at no charge by Shin-Kowa Pharma Company (Tokyo, Japan) (see letter from company president [name]).* During the treatment period, participants will be seen by the research coordinator and/or one of the study investigators every week. At each check in meeting, treatment compliance will be documented in a supplement accountability log based on the unused pill count and participant interview. These visits will also be used to address any study-related issues and help ensure body weight and physical activity remain constant during the study to avoid any potential confounding effects on the outcome measures. All testing conducted at baseline will be repeated after 16 weeks of treatment, and treatment will be continued until all repeat testing is completed. Metabolic testing performed during baseline visits 1 and 3 will be repeated in the same order after the 16-week treatment period.

Participants will be assigned a subject ID number upon entry to the study. The study ID is not related information about the individual and is not capable of being translated so as to identify the individual. Data and biological samples collected from study participants during the study participation will be labeled with the study ID and will *not* be used in combination with any personal identifiable information (PII). All data collected during the study will be de-identified and will not be used with any personal identifiable information.

C.3.1. Study outcomes. The effect of NMN therapy on the following outcomes will be assessed:

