a. Primary outcome: in vivo muscle insulin sensitivity: Skeletal muscle (stimulation of glucose disposal) insulin sensitivity, assessed by using a hyperinsulinemic-euglycemic clamp procedure in conjunction with stable isotopically-labeled glucose tracer infusions [30-32].

b. Secondary outcomes:

i) Body composition analyses: Total body fat mass and fat-free mass will be determined by using dual energy X-ray absorptiometry (DXA), and intra-abdominal adipose tissue volume, intrahepatic triglyceride

content, and hepatic fibrosis will be assessed by using magnetic resonance imaging (MRI) and magnetic resonance elastography (MRE).

ii) β -cell function: Insulin secretion rate and plasma insulin concentration assessed by using modified 3-h oral glucose tolerance test, in conjunction with a measure of insulin sensitivity obtained by using the hyperinsulinemic-euglycemic clamp procedure. β -cell function in response to non-glucose stimuli will be assessed by using the Arginine stimulation test.

iii) Pharmacokinetics of NMN and NAD⁺: NMN concentration or NMN metabolites in plasma, and NAD⁺ concentration in PBMCs, muscle and adipose tissue will be obtained at baseline and after 16 weeks of placebo or NMN treatment. Blood for plasma NMN, PBMC, muscle and adipose tissue will be obtained 60 minutes after ingesting placebo or NMN capsules during basal stage of post-treatment clamp procedure. NMN pharmacokinetics after the first dose of NMN will be assessed after completing all metabolic testing during baseline visit 2 and will be repeated at the end of the study.

iv) Targeted metabolomics: Plasma, muscle and adipose tissue metabolites: a) NAD⁺ content and NAD⁺-related metabolites (nicotinamide, nicotinic acid, NMN, NR, tryptophan, N-methylnicotinamide, ATP), b) markers of insulin resistance (branched-chain amino acids, total amino acids, and acylcarnitines) will be determined by using established high-performance liquid chromatography (HPLC) and liquid chromatography-mass spectrometry (LC-MS) based methods.

v) Mitochondrial function: i) *ex vivo* muscle mitochondrial respirometry; and ii) cellular analysis of mitochondrial proteins (Western blot), NAD⁺ and ATP contents (HPLC/LC-MS), and gene expression (Real-time PCR and RNA-seq) of proteins involved in mitochondrial electron transport chain activity and oxidative metabolism in skeletal muscle biopsy samples.

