b. Muscle and adipose tissue biopsies. Abdominal subcutaneous adipose tissue and vastus lateralis muscle tissue and thigh fat samples will be obtained during the basal period, and subcutaneous adipose tissue and vastus lateralis muscle tissue samples from the opposite leg will also be obtained during insulin infusion of the clamp procedure. To obtain abdominal subcutaneous adipose tissue, the periumbilical area on one side of the body will be cleaned and anesthetized with 1% lidocaine, then a small skin incision (~0.5 cm) will be made in the skin and a small liposuction cannula will be inserted into the incision to aspirate ~2-4 grams of subcutaneous adipose tissue under sterile conditions. The samples will be rinsed immediately in ice-cold saline and cleaned of connective tissue and blood, and submerged in liquid nitrogen and stored at -80 °C until further processing. To obtain skeletal muscle tissue, the site will be cleaned and anesthetized with 2% lidocaine, and then a small incision (~0.5 cm) will be made in the skin. A muscle sample will be obtained by percutaneous biopsy under sterile conditions. Muscle tissue samples will be rinsed immediately in ice-cold saline and cleaned of connective tissue and blood. Most of the tissue will be submerged in liquid nitrogen, and then stored at -80 °C until further processing for protein content, gene expression and metabolomics. One aliquot of fresh muscle tissue obtained during the basal period will be used for high resolution respirometry, conducted on permeabilized muscle fibers by using the Oroboros Oxygraph-2k system. We found that NMN-treated mice increase mitochondrial respiratory function in skeletal muscle by using the same assay system [14]. Respiration in the non-phosphorylative, “Leak”, state is measured in the presence of malate (1 mM), glutamate (10 mM) and pyruvate (5 mM). After stable Leak state measurements are made, oxygen consumption during the oxidative phosphorylation state (OxPHOS) is determined by adding ADP (5 mM) and succinate (10 mM).

If taking certain medications that affect study outcome measures (e.g., steroids) or increase the risk of study procedures (non-steroidal anti-inflammatories e.g. ibuprofen), participants will be asked to temporarily (approximately 7-14 days) discontinue the medications for the study visits.

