c. NMN pharmacokinetics. NMN concentration or NMN metabolites in plasma, and NAD⁺ concentration in PBMCs, muscle and adipose tissue will be obtained at baseline and after 16 weeks of placebo or NMN treatment. Blood for plasma NMN, PBMC, muscle and adipose tissue will be obtained 60 minutes after

ingesting placebo or NMN capsules during the basal period of the hyperinsulinemic-euglycemic clamp procedure performed after 16-week treatment period.

d. Arginine stimulation test. After completing the hyperinsulinemic-euglycemic clamp procedure, an Arginine bolus infusion will be given over 1 minute, followed by blood sampling every 2 min for 10 min to assess maximal β -cell function.

Sleep monitoring. Wrist actigraphy with concurrent light exposure (Actiwatch Spectrum Pro; Philips Respironics) will be used to assess total sleep time during the 7-10 day period before and after 16 weeks of treatment period. Participant will also be asked to complete a sleep journal during this monitoring period.

Sleep questionnaire. Participants will be asked to take answer a questionnaire about their sleep quality.

C.3.2.2. Baseline Visit 2

a. Body composition analyses. In the afternoon of admission, intra-abdominal adipose tissue volume, intrahepatic triglyceride content, and liver fibrosis will be assessed by magnetic resonance imaging (MRI) and magnetic resonance elastography (MRE) [34]. These tests might be scheduled on different days as separate visits or in combination with another visit if necessary.

If a participant has claustrophobia, they will be given the option of taking a benzodiazepine (Ativan or Xanax) pre-procedure which will be dispensed through BJC Pharmacy. If a participant does agree to take the benzodiazepine, prior to the prescription his/her medical history will be reviewed by a study physician. If a participant does take a benzodiazepine during MRI scan, he/she will be required to have a ride home by a caregiver after the visit and to avoid alcohol or other sedating agents overnight.

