C.3.5. Accountability of dispensing placebo and NMN capsules. A Supplement Accountability Log will be used to document the dispensing of the dietary supplement or placebo to the participant and the return of unused product by the participant to WU. The Supplement Accountability Log will document the participant ID, the amount of supplement and the date supplement was dispensed to the participant, and the amount of supplement and date that the study participant returned. Participants will be instructed to return unused supplement at every scheduled WU study visit and study end at WU. The study research coordinator will perform a pill count and document in the Supplement Accountability Log at each WU study visit.

C.3.6. Data safety monitoring. All participants will be contacted by the research coordinator and/or research nurse weekly throughout the study. All safety and medical issues will be reviewed by [name], and, if needed, will be discussed with the participant's primary physician.

C.3.7. Repeat testing. All studies performed at baseline will be repeated after participants complete at least 16 weeks of treatment. Daily placebo or NMN dosing will continue throughout the repeat testing period, which will take ~2 weeks (weeks 16-18 of treatment).

C.3.8. Calculations.

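### Week-16 clamp-day blood and tissue are taken 60 minutes after a capsule and baseline samples after none, so they measure 16 weeks of dosing plus that morning's dose; a pre-dose blood contrast should be prespecified

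*Combined protocol and SAP*

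**What the plan says.** **Baseline.** The clamp and biopsies are at Visit 1, before any study pill. In the Overview, "Visit 3 is another inpatient visit that involves a modified 3-h oral glucose tolerance test and the first dose of study pill ingestion". Section C.3 adds: "After participants complete baseline testing, they will be randomly assigned to treatment with either placebo or NMN".

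**Week 16.** C.3.1.b.iii says that blood for plasma NMN and PBMC, and muscle and adipose tissue, "will be obtained 60 minutes after ingesting placebo or NMN capsules during basal stage of post-treatment clamp procedure". C.3.2.1.c counts the same 60 minutes from "ingesting placebo or NMN capsules during the basal period of the hyperinsulinemic-euglycemic clamp procedure performed after 16-week treatment period". The biopsies also serve other outcomes; in C.3.2.1.b, "One aliquot of fresh muscle tissue obtained during the basal period will be used for high resolution respirometry".

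**Known acute effect.** Section A reports on a single 250 mg dose in people. Within 60 minutes it "caused more than a 3-fold increase in peripheral blood mononuclear cell (PBMC") NAD+ content, and it raised plasma NMN briefly. The trial doses are 300 or 450 mg/day. For tissue, Section A cites acute and short-term NAD+ increases in rodents, without a size.

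**Separate blood series.** C.3.2.3.b (Visit 3) takes blood for plasma NMN and PBMC NAD+ before the first dose and 10, 20 and 60 minutes after it. C.3.1.b.iii places this first-dose work "during baseline visit 2 and will be repeated at the end of the study".

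**Analysis.** Section D specifies ANCOVA of the post-treatment value, adjusted for the pre-intervention value. It does not say which week-16 sample is the post-treatment value for NAD+, and names no pre-dose or first-dose contrast.

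**The concern.** The baseline and week-16 samples differ in two respects in the NMN arm: 16 weeks of daily dosing, and a dose taken one hour earlier. Placebo controls for the capsule and for time, but not for NMN taken that morning. An arm difference in clamp-day NAD+ can therefore come from lasting change, from the morning's dose, or from both.

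What is at stake is interpretation. If a clamp-day PBMC NAD+ difference were presented as evidence that 16 weeks of supplementation raised NAD+ durably, the conclusion would not follow. The same caution applies to basal-biopsy results: NAD+ and related metabolites, respirometry, gene expression and protein acetylation.

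**Working it through.** **The plan's own figures first.** For insulin-mediated glucose Rd, a difference of 6.2 with SD 6.1 gives d = 6.2/6.1 = 1.016. A two-sample t-test at two-sided alpha 0.05 and 90% power needs 21.35, so 22 per group (power 0.909 at 22). Allowing for dropout, 22/(1 − 6/28) = 28. For gene expression, 30.5/30 = 1.017 also gives power 0.909. The plan's numbers reproduce, and none depends on the timing of the capsule.

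**What each contrast estimates.** Let S be the sustained effect of 16 weeks on the pre-dose level, A the acute effect 60 minutes after a dose, and R what remains of the previous daily dose at a pre-dose sample. Taking effects as additive on the analysis scale:

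| Contrast, NMN minus placebo | Estimates |
|---|---|
| Clamp-day sample, week 16 (blood, muscle, fat) | S + A, plus any R |
| Pre-dose sample, end-of-study series (blood) | S + R |
| Rise from pre-dose to 60 min, first dose (blood) | A at first dose |
| Rise from pre-dose to 60 min, week 16 (blood) | A after 16 weeks |

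Blood has all four rows; muscle and fat have only the first. No biopsy is planned after a first dose, or in an undosed state at week 16.

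**PBMC NAD+ with no sustained effect.** Set S = 0 and R = 0. The expected clamp-day contrast is then A. If the acute response at week 16 resembles the pilot's, the NMN arm would be more than 3 times placebo, that is, more than +200%, with no lasting change. This assumes that the response to 300 or 450 mg is at least that to 250 mg and does not alter with repeated dosing.

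**How many week-16 values.** If the repeat series keeps all four time points, PBMC NAD+ has five candidate values at week 16: the clamp-day sample and 4 from the series. Section D does not choose among them.

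**Tissue, as illustration only.** Suppose a fraction f of a +200% rise reaches tissue NAD+ within the hour, and S = 0. With 22 per group and a two-sided t-test at 0.05 on week-16 values, the noncentrality is (200f/SD) × √(22/2). The probability of a significant arm difference is:

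| f | Acute rise | SD 30% | SD 60% |
|---|---|---|---|
| 5% | 10% | 0.19 | 0.08 |
| 10% | 20% | 0.58 | 0.19 |
| 15% | 30% | 0.90 | 0.37 |
| 25% | 50% | about 1.00 | 0.77 |

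For f = 15% and SD 30%, the noncentrality is (30/30) × √11 = 3.32. The 30% SD is the plan's gene-expression figure, borrowed for NAD+. The values of f and the 60% SD are assumptions, because the documents give no acute effect in human tissue.

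**The case against.** The strongest reply is that on-treatment measurement is the design. Dosing is daily and C.3.7 continues it throughout repeat testing. The objective is the effect of NMN supplementation, with no commitment to a trough level. The 60-minute timing is disclosed in both places, one of them under a pharmacokinetics heading. The arms are randomised and sampled alike. All of this stands: the contrast is valid for on-dose treatment, and the clamp-day value should be kept. It does not show that the effect is sustained.

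Three stronger readings are tempting and are not supported.

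- A reader might infer that NAD+ outcomes cannot show a 16-week effect at all. For blood that is wrong, because the first-dose series has a pre-dose sample and C.3.1.b.iii says the work is repeated at the end of the study.
- A reader might infer a proven acute spike in muscle and fat. In people it is documented only for plasma NMN and PBMC NAD+. Nothing shows that gene expression, acetylation or respirometry shifts within an hour.
- A reader might see a contradiction with C.3.7, which says "All studies performed at baseline will be repeated after participants complete at least 16 weeks of treatment". There is none. The next sentence of C.3.7 says dosing continues, and baseline testing precedes treatment.

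It is also fair to say that the pre-dose sample is imperfect. The time points are listed only for the first dose. The first-dose sample follows the oral glucose test, so it is not a fasting sample. At week 16 the time since the previous capsule is not stated. C.3.2 also lets tests be reordered. These points limit the added contrast but do not remove its value.

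**Conclusion.** The point holds in a limited form. Clamp-day NAD+ and basal-biopsy outcomes at week 16 estimate the combined effect of 16 weeks of dosing and that morning's dose. For PBMC NAD+, on the plan's own pilot figure, a difference of more than 3-fold could arise with no sustained effect, provided the acute response persists at week 16. For muscle and fat the acute share is unknown: the illustration runs from negligible to decisive according to assumptions that the documents cannot settle.

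The outcomes concerned are secondary. Nothing here shows bias in the randomised comparison, a fault in the sample size, or a problem with the primary endpoint. The change is nevertheless worth making, because planned blood samples can largely separate the two effects and the analysis section does not call on them.

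**What to change.** 1. In C.3.1.b.iii and Section D, keep the clamp-day value as the on-dose measure, labelled as one hour after a dose. Add a prespecified ANCOVA, for plasma NMN and for PBMC NAD+, of the pre-dose sample in the end-of-study series, adjusted for the Visit 3 pre-dose sample, as the measure of sustained effect. State that the repeat series uses the time points in C.3.2.3.b, and record the time since the previous capsule.
2. Compare the week-16 rise from pre-dose to 60 minutes with the first-dose rise, to show whether the acute response changes with repeated dosing.
3. Report muscle and adipose NAD+, NAD+-related metabolites and the other basal-biopsy outcomes as measured about one hour after a dose, without attributing them to sustained supplementation alone.
4. Reconcile C.3.1.b.iii, which puts first-dose sampling at baseline visit 2, with the Overview and C.3.2.3.b, which put it at Visit 3.

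**Cost.** Specification and reporting text, one recorded time, and no added visit or biopsy. The pre-dose contrast may still carry some of the previous daily dose, and the tissue conclusions become narrower.
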